Statistical Analysis Plan (SAP)

Sweet Tooth: Nature or Nurture? Role of Long-term Dietary Sweetness Exposure on Sweetness Preferences

Version 2024.02.07 (yyyy.mm.dd)

GENERAL INFORMATION	
Principal investigator	Dr. [name] Sensory Science and Eating Behaviour Wageningen University and Research Wageningen, the Netherlands
Core team members	[name] [name] (Project leader) ¹ [name] (statistician) ¹ [name] ² [name] ¹ [name] ² [name] ² [name] ¹
	¹ Division of Human Nutrition and Health, Wageningen University and Research, Wageningen, The Netherlands
	² Department of Psychology, Faculty of Science and Technology, Bournemouth University, Bournemouth, United Kingdom
Name of project	Sweet Tooth
ClinicalTrials.gov identifier	NCT04497974
Project Registration number	NL72134.081.19
Ethical review	METC-nr 20/02, METC-WU

INTRODUCTION	
Objectives	
Primary objective: To assess the effect of a 6-month low, regular, and high dietary sweetness exposure on preference for sweet foods and beverages, and to compare these effects between the intervention groups.
 
Secondary Objective(s): To assess the effect of a 6-month low, regular, and high dietary sweetness exposure on taste intensity perception, behavioural outcomes: food choice and intake, sweet-like type, food cravings, dietary taste preferences, dietary taste patterns; anthropometric outcomes: body composition, waist-hip circumference, body weight; and biochemical outcomes: glucose variability, and biomarkers related to CVD and diabetes.

STUDY METHODS	
Trial design	
The Sweet Tooth study is a 6-month parallel randomized controlled trial with partial food provision. with three arms:
 
 1. a regular sweet exposure diet (RSE, control) (n=60); 2. a low sweetness exposure diet (LSE) (n=60); and 3. a high sweetness exposure diet (HSE) (n=60).
Randomization	
Data collected at the screening visit are used to assign participants to intervention groups. Matched groups are randomized to the interventions to minimize differences between intervention groups in these baseline characteristics. Based on sex (2 levels: male, female), age (3 levels: 18–34, 35–49, 50–65), Body Mass Index (BMI) (2 levels: 18.5–24.9, 25–30 kg/m²) and sweet liker phenotype (3 levels: sweet liker, inverted U, sweet disliker), in a process of stratified randomization (2×3×2×3=36 strata). Treatment allocation is performed according to a computer-generated random schedule, at the ratio 1:1:1 to each of the three groups. Treatment allocation is performed by an independent person, not involved in the study outcome assessments or statistical analyses.

Sample size	
The sample size calculation is based on our primary outcome: change in preference score from 0–6 months. Previous studies have established that it is possible to detect shifts in preferred concentration from preference tests. For example, looking at the study of Liem and [name] (2004) and the change in most preferred concentration, we can observe that mean ranking score for the sweet exposure group changed by around 0.4 and by around 0.6 for the sour exposure group from baseline to after exposure, which is around 10%. Therefore, the effect size of 0.1 was considered to be a relevant and meaningful effect size for our study and was used to estimate the sample size. We estimate that 147 participants are needed to detect an effect size of 0.1, assuming a parallel study with 3 groups, with two repeated measures (baseline vs 6-month, correlation between measures of 0.7), and a

	power of 80% at a significance level of 0.05. To account for a potential dropout of 20%, 180 individuals will be enrolled in the study.																																																																																																																																																																																									
Statistical interim analysis	No interim analyses will be carried out.																																																																																																																																																																																									
Timing of final analysis	Statistical analysis will be performed when the last subject leaves the follow up period.																																																																																																																																																																																									
Timing of outcome assessments	
  
 Domain	Outcome to Be Measured	Data Collection Method	Baseline	Intervention	Follow-up	
 
 1 Month	3 Months	6 Months	7 Months	10 Months	
   
 Food taste preference	Sweetness preferences	Rank-rating scale	✓	✓	✓	✓	✓	✓	
 
 	Saltiness preferences		✓	✓	✓	✓	✓	✓	
 
 Taste intensity perception	Sweet taste perception	100-unit VAS	✓	✓	✓	✓	✓	✓	
 
 	Salt taste perception		✓	✓	✓	✓	✓	✓	
 
 Behavioural outcomes	Food choice	Food choice from a buffet	✓	✓	✓	✓	✓	✓	
 
 	Food intake	Amount consumed from a buffet	✓	✓	✓	✓	✓	✓	
 
 	Sweet-liker type	100-point VAS	✓	✓	✓	✓	✓	✓	
 
 	Taste preferences	PrefQuest^a	✓	✓	✓	✓	✓	✓	
 
 	Food cravings	CoEQ	✓	✓	✓	✓	✓	✓	
 
 	Dietary taste patterns	Taste FFQ^b	✓	✓	✓	✓	✓	✓	
 
 Anthropometric outcomes	Body composition	DEXA	✓			✓		✓	
 
 	Waist-hip circumference	Measuring tape	✓	✓	✓	✓	✓	✓	
 
 	Weight	Digital scale	✓	✓	✓	✓	✓	✓	
 
 Biochemical outcomes	Biomarkers related to CVD and diabetes	Fasting blood sample	✓	✓	✓	✓	✓	✓	
 
 	Glucose homeostasis	Glucose sensor^c	✓			✓		✓	
 
 Compliance	Biomarkers of compliance	Urine sample (24-h sample)	✓	✓	✓	✓	✓	✓	
 
 	Dietary intake	Online 24-h recall	✓	✓	✓	✓	✓	✓	
 
 Intervention Moderators	Physical activity	SQUASH	✓	✓	✓	✓	✓	✓	
 
 	Adverse events, medication use	Questionnaires^b, Study diet diary	✓	✓	✓	✓	✓	✓	
  
 
CoEQ Control of eating questionnaire, CVD Cardiovascular disease, DEXA Dual-energy x-ray absorptiometry, SQUASH Short questionnaire to assess health enhancing physical activity, VAS Visual analogue scale
 
^aTranslated and Modified for the Dutch population based on Degraire et al., 2012
 
^b Developed for the Sweet tooth study based on methodology of Diewertje et al., 2016
 
^c Only in a sub-set of participants (n = 60)
	Domain	Outcome to Be Measured	Data Collection Method	Baseline		Intervention		Follow-up		1 Month	3 Months	6 Months	7 Months	10 Months	Food taste preference	Sweetness preferences	Rank-rating scale	✓	✓	✓	✓	✓	✓		Saltiness preferences		✓	✓	✓	✓	✓	✓	Taste intensity perception	Sweet taste perception	100-unit VAS	✓	✓	✓	✓	✓	✓		Salt taste perception		✓	✓	✓	✓	✓	✓	Behavioural outcomes	Food choice	Food choice from a buffet	✓	✓	✓	✓	✓	✓		Food intake	Amount consumed from a buffet	✓	✓	✓	✓	✓	✓		Sweet-liker type	100-point VAS	✓	✓	✓	✓	✓	✓		Taste preferences	PrefQuest ^a	✓	✓	✓	✓	✓	✓		Food cravings	CoEQ	✓	✓	✓	✓	✓	✓		Dietary taste patterns	Taste FFQ ^b	✓	✓	✓	✓	✓	✓	Anthropometric outcomes	Body composition	DEXA	✓			✓		✓		Waist-hip circumference	Measuring tape	✓	✓	✓	✓	✓	✓		Weight	Digital scale	✓	✓	✓	✓	✓	✓	Biochemical outcomes	Biomarkers related to CVD and diabetes	Fasting blood sample	✓	✓	✓	✓	✓	✓		Glucose homeostasis	Glucose sensor ^c	✓			✓		✓	Compliance	Biomarkers of compliance	Urine sample (24-h sample)	✓	✓	✓	✓	✓	✓		Dietary intake	Online 24-h recall	✓	✓	✓	✓	✓	✓	Intervention Moderators	Physical activity	SQUASH	✓	✓	✓	✓	✓	✓		Adverse events, medication use	Questionnaires ^b , Study diet diary	✓	✓	✓	✓	✓	✓
Domain	Outcome to Be Measured				Data Collection Method	Baseline		Intervention		Follow-up																																																																																																																																																																																
		1 Month	3 Months	6 Months		7 Months	10 Months																																																																																																																																																																																			
Food taste preference	Sweetness preferences	Rank-rating scale	✓	✓	✓	✓	✓	✓																																																																																																																																																																																		
	Saltiness preferences		✓	✓	✓	✓	✓	✓																																																																																																																																																																																		
Taste intensity perception	Sweet taste perception	100-unit VAS	✓	✓	✓	✓	✓	✓																																																																																																																																																																																		
	Salt taste perception		✓	✓	✓	✓	✓	✓																																																																																																																																																																																		
Behavioural outcomes	Food choice	Food choice from a buffet	✓	✓	✓	✓	✓	✓																																																																																																																																																																																		
	Food intake	Amount consumed from a buffet	✓	✓	✓	✓	✓	✓																																																																																																																																																																																		
	Sweet-liker type	100-point VAS	✓	✓	✓	✓	✓	✓																																																																																																																																																																																		
	Taste preferences	PrefQuest ^a	✓	✓	✓	✓	✓	✓																																																																																																																																																																																		
	Food cravings	CoEQ	✓	✓	✓	✓	✓	✓																																																																																																																																																																																		
	Dietary taste patterns	Taste FFQ ^b	✓	✓	✓	✓	✓	✓																																																																																																																																																																																		
Anthropometric outcomes	Body composition	DEXA	✓			✓		✓																																																																																																																																																																																		
	Waist-hip circumference	Measuring tape	✓	✓	✓	✓	✓	✓																																																																																																																																																																																		
	Weight	Digital scale	✓	✓	✓	✓	✓	✓																																																																																																																																																																																		
Biochemical outcomes	Biomarkers related to CVD and diabetes	Fasting blood sample	✓	✓	✓	✓	✓	✓																																																																																																																																																																																		
	Glucose homeostasis	Glucose sensor ^c	✓			✓		✓																																																																																																																																																																																		
Compliance	Biomarkers of compliance	Urine sample (24-h sample)	✓	✓	✓	✓	✓	✓																																																																																																																																																																																		
	Dietary intake	Online 24-h recall	✓	✓	✓	✓	✓	✓																																																																																																																																																																																		
Intervention Moderators	Physical activity	SQUASH	✓	✓	✓	✓	✓	✓																																																																																																																																																																																		
	Adverse events, medication use	Questionnaires ^b , Study diet diary	✓	✓	✓	✓	✓	✓																																																																																																																																																																																		

OUTCOMES		
Primary Outcome measure		
Outcome Measure	Measure Description	Time Frame
Change in preference score	Measured during preference testing, using Ranking on a scale methodology (scale anchored at 0: Dislike extremely; 50: Neither dislike or like; 100: Like extremely) in a series of test foods.	From month 0 to month 6.
Secondary Outcome measures		
Outcome Measure	Measure Description	Time Frame
Change in preference score.	Measured during preference testing, using Ranking on a scale methodology (scale anchored at 0: Dislike extremely; 50: Neither dislike or like; 100: Like extremely) in a series of test foods.	Measured at 0, 1, 3, 6, 7 and 10 months.
Difference in mean liking scores between familiar and unfamiliar foods.	Measured during preference testing, using Ranking on a scale methodology (scale anchored at 0: Dislike extremely; 50: Neither dislike or like; 100: Like extremely) in a series of test foods.	Measured at 0, 1, 3, 6, 7 and 10 months.
Change in sensory intensity scores.	Measured during sensory testing, using 100-unit Visual analogue scale (VAS), (anchored at 0: not sweet/salty at all; 100: Extremely sweet/salty) in a series of test foods.	Measured at 0, 1, 3, 6, 7 and 10 months.
Change in energy intake.	Measured during ad-libitum test meal in kcal.	Measured at 0, 1, 3, 6, 7 and 10 months.

Change in energy intake.	Measured during ad-libitum test meal in kJ.	Measured at 0, 1, 3, 6, 7 and 10 months.
Proportion of eaten sweet foods vs. foods from other taste modalities.	Measured during ad-libitum test meal in proportions.	Measured at 0, 1, 3, 6, 7 and 10 months
Sweet-liker status score.	Measured on a 100-unit VAS scale (anchored at 0: Dislike; 100: Like).	Measured at 0, 1, 3, 6, 7 and 10 months.
Food craving questionnaire scores.	Measured using the Control of eating questionnaire (CoEQ)	Measured at 0, 1, 3, 6, 7 and 10 months.
Taste preference questionnaire scores.	Measured using Taste Preference questionnaire (PrefQuest).	Measured at 0, 1, 3, 6, 7 and 10 months.
Dietary taste patterns.	Measured with the Taste food frequency questionnaire in frequency.	Measured at 0, 1, 3, 6, 7 and 10 months.
Dietary taste patterns.	Measured with the Taste food frequency questionnaire in % of energy coming from each taste cluster.	Measured at 0, 1, 3, 6, 7 and 10 months.
Dietary taste patterns.	Measured with the Taste food frequency questionnaire in % of food weight coming from each taste cluster.	Measured at 0, 1, 3, 6, 7 and 10 months.
Body weight.	Measured with a weighing scale in kg.	Measured at 0, 1, 2, 3, 4, 5, 6, 7 and 10 months.
Waist-to-hip ratio.	Measured using a stretch-resistant tape.	Measured at 0, 1, 3, 6, 7 and 10 months.
% of body fat mass and lean body mass (fat free mass).	Measured with a dual energy x-ray absorptiometry (DEXA).	Measured at 0, 6 and 10 months.
Variation in interstitial glucose levels.	Measured with glucose monitoring sensor (only measured in a subgroup, of 60 subjects, 20 per intervention arm).	Measured at 0, 6 and 10 months.
Change in fasting glucose, HbA1c, insulin, total cholesterol, low-density lipoprotein (LDL), high-density lipoprotein (HDL), triglycerides levels in blood.	Measured in blood in mmol/L.	Measured at 0, 1, 3, 6, 7 and 10 months.
Concentration of biomarkers in urine related to sugar, low and no calorie sweeteners, protein and salt intake.	Measured in urine in mg/d.	Measured at 0, 1, 3, 6, 7 and 10 months.
Intake levels of foods, food groups and macronutrients.	Measured with 24-hour recalls, in kcal/day.	Measured at 0, 1, 2, 3, 4, 5, 6, 7 and 10 months.
Other Outcome measures		
Outcome Measure	Measure Description	Time Frame
Adverse events.	Self-reported and monitored.	Measured at 0, 1, 2, 3, 4, 5, 6, 7, 8, 9 and 10 months.
Gender.	Self-reported.	Assessed at month 0.
Height.	Measured with a stadiometer.	Assessed at month 0.
Physical activity level.	Measured with the Short Questionnaire to Assess Health enhancing physical activity (SQUASH).	Measured at 0, 1, 3, 6, 7 and 10 months.
Polymorphisms related to sweet taste perception.	Genes will be extracted from collected blood samples.	Assessed at month 0.
Age.	Self-reported.	Assessed at month 0.
Medicine usage.	Number and type of medicine used, self-reported.	Assessed at month 0.

STATISTICAL PRINCIPALS	
Principals and P-values	Prior to data analysis, normality of the data will be inspected. Non-normally distributed data will be transformed or analysed using non-parametric tests, if deemed necessary. Statistical significance is set at $p<0.05$.
Adherence and Protocol deviations	Adherence to diets will be assessed on group level with biomarkers of sweetener consumption in 24-h urine sample, and 24h recalls.

STATISTICAL ANALYSIS	
Analysis methods	
Data will be analyzed in R. Based on findings of previous studies (Liem and [name], 2004), we do not expect the data to be non-normally distributed. Descriptive statistics will be provided for each of the three intervention groups at baseline and will include demographic, dietary and lifestyle information. Continuous data will be summarized using means, SD/SE and 95% confidence intervals or median/geometric means and back-transformed 95% CI's if not normally distributed. Categorical variables will be summarized using counts and percentages.
 
Analysis will be conducted on both an intention-to- treat (ITT) and a per-protocol basis. The ITT analysis will be the primary analysis. The per-protocol analysis (participants who finished the study), will help us determine whether the effects are the result of individuals adhering to the procedure and consuming the provided intervention foods. In the event of missing data due to drop-out, the outcome variables that have not been recorded will be treated as missing data. Unblinding will occur at the conclusion of the study to determine the effect of the intervention. Unblinding will take place in two steps: initially disclosing the allocation of individuals to their respective groups, without indicating intervention allocation. Only after the primary analyses have been conducted we will unblind the identity of each group.
 
Primary outcome:
 
To determine whether there is a shift in sweetness preference between baseline and month 6, statistical techniques appropriate for longitudinal data analysis, that is linear mixed effects models, will be used, with treatment (LSE, RSE and HSE), time (baseline, 1, 3, 6, 7 and 10-months) as fixed factors, the interaction between treatment x time outcome and participant number as a random factor. Our main interest is in the change in preference score between 0 and 6 months of any two intervention groups. The interaction effect will be evaluated to indicate if the change differed between the groups. If significant, the following predefined contrasts will be calculated: baseline vs. month 6 and LSE vs. RSE vs. HSE with all possible combinations. Subsequent, pairwise post-hoc tests will be Bonferroni adjusted.

Other outcomes:

Similar linear mixed effects models will be used to explore effects of sweet taste exposure on the other dependent measures over time (baseline, 1, 3, 6, 7 and 10-months). The interaction effect (intervention group x time) will be evaluated to indicate if the pattern of change of a certain outcome differed between the groups. If significant, the following predefined contrasts will be calculated: baseline vs. 1 vs. 3 vs. 6 vs. 7 vs. 10-months and LSE vs. RSE vs. HSE with all possible combinations.

In light of the research in this area, we will explore differences between intervention groups and secondary outcome variables and explore related but separate questions of whether glucose variability, body composition, food cravings, blood biomarkers are related to sweetness exposure, age, gender, sweet liker status and BMI.

By comparing group means of urine extraction of urinary sucrose, fructose, and LCSs between intervention groups, the level of compliance will be evaluated. Linear mixed effects models will be adjusted for covariates where appropriate and both unadjusted and adjusted models will be reported. If interaction effect between time and intervention are identified, Posthoc tests (with Bonferroni adjustments) will be applied to identify statistically significant differences.

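### Enrolling 180 does not retain the 147 participants the SAP says it needs if 20% drop out: 144 complete, a small shortfall that calls for a corrected sentence

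*SAP*

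**What the plan says.** The Sample size section (under Study Methods) gives the requirement as: "We estimate that 147 participants are needed to detect an effect size of 0.1". The design behind that number is "assuming a parallel study with 3 groups", "with two repeated measures (baseline vs 6-month, correlation between measures of 0.7"), with "power of 80% at a significance level of 0.05". The step to enrolment is: "To account for a potential dropout of 20%, 180 individuals will be enrolled in the study".

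The Trial design section repeats 180 as three arms of 60, and the Randomization section allocates "at the ratio 1:1:1 to each of the three groups". The Analysis methods section makes the intention-to-treat analysis primary, fits a linear mixed model with participant as a random factor and baseline as one level of time, and leaves unrecorded outcomes missing. Nothing else in the SAP explains how 147 became 180.

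**The concern.** Dropout is a fraction of the people enrolled. If one in five of 180 leaves, 36 are lost and 144 finish, which is below the number that the same paragraph says is needed. The requirement, the dropout rate and the enrolment figure therefore cannot all be right as a statement about completers.

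The issue is the accuracy of the sample-size justification. A reader would take the sentence to mean that the trial can lose a fifth of its participants and still have the stated number of complete 0–6 month pairs. It would fall slightly short.

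**Working it through.** **Inputs, all from the SAP.** Required number 147; dropout 20%; enrolment 180 (60 per arm); 3 groups; 1:1:1 allocation; effect size 0.1; 2 measures with correlation 0.7; target power 80%; significance level 0.05. The SAP does not name the type of effect size. I take it as Cohen's f, which is an assumption.

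**1. Reproducing 147.** For the group-by-time interaction in a repeated-measures analysis, the noncentrality is λ = f² × N × m / (1 − ρ), with 2 and N − 3 degrees of freedom.

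| N | λ = 0.01 × N × 2 / 0.3 | Power |
|---|---|---|
| 144 | 9.60 | 78.9% |
| 147 | 9.80 | 79.8% |
| 148 | 9.87 | 80.1% |

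The smallest N that reaches 80% is 148, so 147 is reproduced to within one participant. The other two tests in this family do not fit: the between-group test would need 822 and the within-group test 120. The interaction test, with 0.1 read as Cohen's f, is therefore the likely source.

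**2. The dropout step.**
- Completers at 20% loss: 180 × 0.80 = 144, or 60 × 0.80 = 48 per arm. The requirement is 147 / 3 = 49 per arm. The gap is 3 in total, 1 per arm.
- Enrolment that keeps 147: 147 / (1 − 0.20) = 183.75, so 184. With equal arms, 49 / 0.80 = 61.25, so 62 per arm and 186 in total.
- Largest loss that 180 can absorb: 1 − 147 / 180 = 18.3%.
- For comparison, adding 20% to the requirement gives 147 × 1.2 = 176.4, or 58.8 per arm, which would round up comfortably to 60. That may be how 180 arose, but the SAP does not say so and the point does not depend on it.

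**3. Effect on the planned primary analysis.** The table in step 1 counts only people with both measures. The mixed model also uses baseline values from those who leave. Take 48 completers and 12 baseline-only participants per arm, data missing at random, correlation 0.7 and unit variance. The variance of the estimated 0–6 month mean change in an arm is then

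(1 − ρ²)/48 + (1 − ρ)²/60 = 0.51/48 + 0.09/60 = 0.010625 + 0.0015 = 0.012125.

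With n complete pairs it is 2(1 − ρ)/n = 0.6/n. Setting the two equal gives n = 0.6 / 0.012125 = 49.5 per arm, about 148 in total. By step 1 that corresponds to power of about 80%.

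If the dropouts were also seen at later visits, more is recovered. Under a random-intercept model with the same correlation, the equivalent is 51.0 pairs per arm if all 12 were seen at months 0 and 1, and 50.8 if departures are spread evenly after months 0, 1 and 3.

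**The case against.** The strongest reply is that the shortfall disappears under the analysis actually planned. The primary model keeps every recorded visit, so a participant who leaves early still carries some information. Even when all dropouts leave straight after baseline, the equivalent number of complete pairs is 49.5 per arm, above the 49 behind the requirement. This stands, given data missing at random and the plan's own correlation. It rules out a stronger reading that a reader might infer: that 180 enrolled, 20% dropout and 80% power are incompatible. They are incompatible only on a completers-only calculation.

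It does not rescue the sentence. The sample-size calculation is built on two measures per person and takes no credit for partial data, so its dropout allowance has to be read in complete pairs. The per-protocol analysis, restricted to participants who finished, is also directly affected.

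A second reply is that the SAP does not say when the 20% is lost. Follow-up continues to month 10, while the primary outcome ends at month 6, and anyone lost after month 6 still supplies it. That is correct, and the figure of 144 assumes that all the loss falls before month 6. The corrected text should state the time point.

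A third reply is that the gap is trivial: 3 people and 0.9 of a percentage point, set against a dropout rate that is itself a guess and a requirement that gives 79.8% on recalculation. This is accepted as to size. It bears on how much weight the point deserves, and the arithmetic is still wrong as written.

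**Conclusion.** The dropout allowance is misstated. Enrolling 180 and losing 20% before month 6 leaves 144 completers against a stated need of 147. The most that 180 can lose while keeping 147 is 18.3%. This part is exact and needs no assumption beyond the timing of the loss.

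The consequence is minor. Power on the completers-only calculation is 78.9% instead of 79.8%, taking 0.1 as Cohen's f. Under the planned mixed model it stays near 80% if data are missing at random, the correlation is 0.7 and losses are balanced across arms. The SAP's figures do not support saying that the trial is underpowered because of this step, or that more people must be recruited.

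**What to change.** Keep 180 and replace the dropout sentence with one of two statements:

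- enrolling 180 retains 147 participants with both measures at up to about 18% dropout by month 6; or
- 20% dropout by month 6 leaves 144 completers, with about 79% power on the two-measure, completers-only calculation.

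If the second is chosen, name the effect size as Cohen's f (if that is what was used). Add that the primary mixed model also uses the visits recorded before dropout, so that the 79% is not read as the power of the primary analysis.

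The cost is one or two sentences in the Sample size section. Enrolment, allocation and analysis do not change. Raising enrolment to 184 or 186 would also reconcile the figures, but a gap of this size does not call for it.

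### The primary model leaves each arm its own baseline mean; one common baseline mean would cut the variance of the month 0 to 6 between-arm contrast by about 15% at no cost in data

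*SAP*

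**What the plan says.** Under Analysis methods, Primary outcome, the SAP specifies a linear mixed model "with treatment (LSE, RSE and HSE), time (baseline, 1, 3, 6, 7 and 10-months) as fixed factors", with their interaction and participant as a random factor. It then says: "Our main interest is in the change in preference score between 0 and 6 months of any two intervention groups". The interaction test acts as a gate: "If significant, the following predefined contrasts will be calculated: baseline vs. month 6 and LSE vs. RSE vs. HSE with all possible combinations". Pairwise tests after it are Bonferroni adjusted.

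The Sample size entry works on the same footing, "assuming a parallel study with 3 groups, with two repeated measures (baseline vs 6-month, correlation between measures of 0.7"), and concludes that "147 participants are needed to detect an effect size of 0.1". The Randomization entry describes stratified 1:1:1 allocation.

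Nothing constrains the baseline means of the arms to be equal or adjusts the primary model for the baseline score. The one sentence on covariate adjustment stands under Other outcomes and names no covariate.

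**The concern.** With three arms, six visits and a full interaction, the model has 3 x 6 = 18 free means, three of them at baseline. Randomisation makes those three equal in expectation, so the model estimates two differences already known to be zero. The price is paid in the contrast of main interest: each arm's month 6 mean is set against its own noisy baseline mean, as in a comparison of raw change scores.

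Three results are affected: the between-arm month 0 to 6 contrasts, the within-arm baseline to month 6 contrasts, and, to a degree that depends on the time course, the six-visit interaction test that must be significant before any contrast is calculated.

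**Working it through.** **Inputs from the SAP (Sample size; Analysis methods).** Three arms; correlation rho = 0.7; significance level 0.05; power 80%; N = 147; effect size 0.1; 180 enrolled with 20% dropout; six visits.

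**Assumptions.** Effect size read as the F-test effect size f; a random participant intercept, hence equal correlation between all visits; unit variance; month 0 scores taken before the diets start. The SAP gives no time course, so several are tried.

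**The plan's own figure.** For the repeated-measures interaction test with two visits, lambda = N x f² x 2/(1 - rho) = 147 x 0.01 x 2/0.3 = 9.80, on 2 and 144 df. Power is 79.8%, and 80% is reached at N = 148. The stated 147 is thus reproduced to within one participant. This test is a test of raw changes.

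**Between-arm variance factor, month 0 to 6**
- Free baseline means: 2(1 - 0.7) = 0.60
- Common baseline mean: 1 - 0.7² = 0.51
- Ratio 0.51/0.60 = 0.85, 15% lower

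**Within-arm change**
- Free: 0.60
- Common: 0.51 + (1 - 0.7)²/3 = 0.54, 10% lower

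**With 20% dropout.** Variance of the month 6 between-arm contrast, scaled to one participant per arm:

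| Leaving | Free | Common | Saving |
|---|---|---|---|
| None | 1.200 | 1.020 | 15.0% |
| Right after baseline | 1.455 | 1.275 | 12.4% |
| Evenly after months 0, 1, 3 | 1.417 | 1.237 | 12.7% |
| All after month 3 | 1.394 | 1.214 | 12.9% |
| Evenly after months 0, 1, 3, 6, 7 | 1.319 | 1.139 | 13.7% |

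The within-arm saving over the same four dropout patterns is 8.2% to 9.1%.

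**Power of the planned gate.** The gate has (3 - 1)(6 - 1) = 10 df, with denominator df (147 - 3) x 5 = 720. The arms are placed at -d, 0, +d at month 6; f = 0.1 corresponds to d = sqrt(6) x 0.1 = 0.245 SD. Complete data, N = 147:

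| Assumed time course | Noncentrality, free / common | Power, free / common |
|---|---|---|
| Month 6 only | 16.33 / 16.55 | 79.7% / 80.3% |
| Months 1, 3 and 6 equally | 29.40 / 31.36 | 98.0% / 98.7% |
| Build-up 1/6, 1/2, 1, then 1/2 and 1/4 at months 7 and 10 | 12.09 / 13.36 | 63.7% / about 69% |
| Constant to month 10 | 16.33 / 21.78 | 79.7% / 91.6% |

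Simulation puts the type I error of the common-baseline gate at 5.0% to 5.1%.

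**Gate, then at least one Bonferroni-significant month 0 to 6 pair** (simulated, three pairs assumed, N = 147): month 6 only, about 70% to 75%; months 1, 3 and 6, 78% to 85-86%; build-up and fade, 60% to 67%; constant, 70% to 82%.

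**Direct 2-df test of month 0 to 6** (not the plan's gate). With the common baseline, lambda = N(2f)²/(1 - rho²) = 147 x 0.04/0.51 = 11.53. Power rises from 79.8% to 86.2%. At 180 x 0.8 = 144 completers it rises from 78.9% to 85.4%. N for 80% power falls from 148 to 126.

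**Sensitivity to the correlation.** With one common rho the complete-data saving is (1 - rho)/2: 25% at 0.5, 15% at 0.7, 10% at 0.8, 5% at 0.9. If the model's common correlation is 0.7 but the true month 0 to 6 correlation is r, the factors are 1.49 - 1.4r (common) and 2(1 - r) (free):
- r = 0.5: 0.79 against 1.00, saving 21%
- r = 0.6: 0.65 against 0.80, saving 19%
- r = 0.8: 0.37 against 0.40, saving 7.5%
- r = 0.85: both 0.30; above this the constraint loses precision

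**The case against.** The strongest reply is that nothing here is an error. The outcome is defined as change, the trial is sized for raw change, and the model analyses change. A treatment by time model with baseline among the responses is standard and valid, and the stated N already carries the factor 0.60. All of this stands, so the point is an improvement and not a correction.

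The 12-point end also needs an effect that persists undiminished to month 10, after the diets have ended. With an effect at month 6 only, or at months 1, 3 and 6 equally, the gate itself gains under 1 point. That stands for the gate alone. It does not stand for the planned sequence, where the month 0 to 6 contrasts gain about 5 points or more in every time course tried.

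The gain also depends on rho. At a common correlation of 0.8, with the same f and N, the gate gains at most about 3 points (constant effect, 94.8% to 98.0%); at 0.9 it gains almost nothing. If scores are averaged over several test foods, the true correlation could exceed 0.7. This is a fair limit on the size, but 0.7 is the plan's own value and the saving is larger below it.

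Finally, with dropout the likelihood fit also uses partial data, so the description as raw changes is exact only for complete data. The saving shrinks slightly, as shown above.

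**Conclusion.** The point holds as a matter of efficiency, not of bias or validity. At the plan's correlation of 0.7 the free baseline means cost 15% in the variance of the between-arm month 0 to 6 contrast (12.4% to 13.7% with the assumed dropout) and 10% in the within-arm change (8.2% to 9.1%). At N = 147 the gate would gain from under 1 to about 12 percentage points of power, and the gate with its Bonferroni contrasts about 5 to 12. The variance figures do not depend on a time course; the power figures do, and on reading 0.1 as f. All of them rest on the equal-correlation structure. The change is worth making because power at 147 is only about 80%, and the Bonferroni contrasts after the gate bring it to about 60% to 78% in the time courses tried.

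**What to change.** Keep the six-visit mixed model with participant as random factor, but constrain the three arms to one common baseline mean. State the gate as the joint 10-df test of all post-baseline treatment differences (5 visits x 2). The within-arm baseline to month 6 contrasts and the pairwise arm contrasts remain available. Report the present model with free baseline means as a sensitivity analysis, and fix this before group allocation is disclosed.

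If the team prefers baseline only as a covariate (baseline score by visit), the gate must become a direct 2-df test of the month 6 treatment differences. In that model the treatment by visit test over months 1 to 10 has 8 df and cannot see a constant effect: its power there is 5%, against 79.7% for the present gate. The SAP would also have to say how the within-arm change is then estimated.

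Optionally, add the four stratification factors as main effects. If they explain an assumed 5% to 20% of score variance, the variance factor falls from 0.51 to between 0.505 and 0.4875, a further 0.9% to 4.4%. It would also help to state whether the covariate sentence under Other outcomes reaches the primary outcome.

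The cost is SAP wording: the constraint, a restated gate and a sensitivity analysis. No new data are needed. The model has 16 mean parameters instead of 18; the optional strata would add 6. It relies on randomisation and on month 0 scores being taken before the diets start, which should be confirmed.
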